#### 5 CORRELATIVE STUDIES FOR RESEARCH

Note: Platforms and procedures for analysis may be adjusted based upon current technology and/or collaborations in place at the time of actual analyses.

#### 5.1 BIOSPECIMEN COLLECTION

Please note that details for collection, processing, storing and shipping will be described in the Trial Lab Manual.

Version Date: 7/10/2025

## **5.1.1** Blood Sample

Blood samples will be collected for all enrolled participants at the time points described in the Specimen Collection Table (Section 5.2).

## 5.1.1.1 Cytokine and immune cell profiling

Peripheral immune cell profiling and cytokine analysis will be performed to determine the effect of Minnelide on the systemic immune environment in ASCP participants. Peripheral immune cells will be analyzed by multiparameter flow cytometry to identify potential changes in 10 classic subsets (CD4 and CD8 T cells, B cells, NK cells, NK-T cells, conventional and plasmacytoid dendritic cells, T regulatory cells, MDSCs, and monocytes) and 121 refined subsets relating to their maturation and function.

## 5.1.1.2 CTCs and circulating tumor DNA (ctDNA)

Analysis of CTCs and ctDNA will be performed to identify potential early biomarkers of response to Minnelide therapy. CTCs will be enumerated and characterized. If CTCs are sufficient, they will be enriched and analyzed for gene expression and mutation. Mutational status of genes in ctDNA including, but not necessarily limited to, KRAS will be evaluated as well as copy number variation of MYC and potentially other genes of interest will be assessed.

#### 5.1.2 Archival Tumor Tissue

All participants will be asked to provide an archival tumor tissue specimen to identify overall mutational landscape of tumor or results of prior tumor mutational analysis by an FDA approved platform (e.g., Foundation One).

If information from genomic mutational analysis previously performed on a participant's tumor sample using another CLIA-certified platform is not available, tissue will be analyzed by NCI Laboratory of Pathology (LP) COMPASS program. Results will be returned to participants. Whole exome sequencing (WES) or whole genome sequencing (WGS) may be performed on selected samples.

A minimum of 10-unstained slides will be requested for TruSight analysis by NCI LP.

#### 5.1.3 Fresh Tumor Tissue/ recent archival tumor tissue

Participants may elect to provide tissue for additional research studies designed to better understand the treatment effect of Minnelide on their tumor. Participants will be provided with the following options to provide tumor tissue for the analyses described below:

- 1. Participants who have had recent core or excisional biopsy of a tumor lesion (within 90 days prior to Cycle 1/Day 1 and since completion of last anti-cancer therapy) may consent to use this tissue for baseline analysis for the purposes of this study even if it was collected for another reason.
- 2. Participants lacking a recent core or excisional biopsy of a tumor lesion may consent to undergo new biopsy of a tumor lesion for research purposes unless tumor is considered inaccessible or biopsy is otherwise considered not in the participant's best interest.
- 3. Participants on study will be asked to consent to biopsy after the completion of 2 weeks of treatment (~Cycle 1 Day 15), and at the time of disease progression unless tumor is considered inaccessible or biopsy is otherwise considered not in the participants best

Version Date: 7/10/2025

interest.

Consent for biopsy will be obtained by the interventionalist at the time of the procedure. If the participant refuses the optional biopsy, the refusal will be documented in the medical record.

Each tumor biopsy will consist of approximately 5 passes, and will be processed, stored and shipped as per the Trial Lab Manual. In case of insufficient tissue to complete all assays described below, priority will be given to completing the analyses listed first in the **Specimen Collection Table**.

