## 5.1.3.6 Establishment of participant-derived xenograft (PDX) and organoid models

PDX/Organoid models will be established by collaborators at TGen if residual tissue remains after other analyses are completed. Those models will be used to study the biology of ASCP and test new therapeutic regimens for ASCP and may also be used to help understand mechanisms of resistance to Minnelide.

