# 5.2 SPECIMEN COLLECTION TABLE

Specimen Type	Test/assay (listed in order of precedence)	Specimen Type (Amount)	Collection (timepoints)	Location of specimen analysis^ (CCR lab database, if applicable)	
Archival or fresh tumor tissue obtained at any time prior to start of study. FFPE acceptable. If multiple acceptable specimens are available, analysis should be completed with the most recent.  (Optional)	Tumor mutational analysis WES or WGS on selected	10-unstained slides If sufficient tissue available after other analyses below	Baseline	NCI LP BPC (TBD*) (Labmatrix)	
Fresh tumor tissue (Optional)	IHC for PD biomarkers ATAC-seq Multiplex IHC for immune cell changes Digital spatial genomics and/ or single cell RNA-seq	Unstained slides; or, 5-18 gauge cores at each timepoint	Baseline Cycle 1 Day 15 (±7 days)	TGen [name]/ [name] (Labmatrix)	
Fresh tumor tissue (Optional)	PDX/ organoid model generation Tumor mutational analysis WES or WGS on selected	2-18g cores	At the time of disease progression	TGen NCI LP BPC (TBD*) (Labmatrix)	

Version Date: 7/10/2025

Specimen Type	Test/assay (listed in order of precedence)	Specimen Type (Amount)	Collection (timepoints)	Location of specimen analysis^ (CCR lab database, if applicable)
Serum	Cytokine markers	1- 4 mL red SST tubes at each timepoint	Baseline Cycle 1 Day 15 (±7 days) At the time of disease progression	BPC ([name]) (Labmatrix)
Blood	ctDNA	1- Streck 10-cc Cell- Free DNA BCT tube for each timepoint	Baseline Cycle 1 Day 15 (±7 days) Cycle 2 Day 1 (±3 days) At the time of disease progression	Developmental Therapeutics Branch Clinical Translation Unit (DTBCTU) (Labmatrix)
Blood	CTCs	2- Streck 10-cc Cell- Free DNA BCT tubes at each timepoint	Baseline Cycle 1 Day 15 (±7 days) Cycle 2 Day 1 (±3 days) At the time of disease progression	DTBCTU (Labmatrix)
PBMC	Immune cell subset profiling by flow cytometry	2 - 10 cc sodium heparin (green top) at each timepoint	Baseline Cycle 1 Day 15 (±7 days)	[name] (Labmatrix)

\*Laboratory for planned analyses has not been finalized. Samples to be retained by the Biospecimen Processing Core (BPC) until distribution. Tube size for bloods may be adjusted based on supply available or change in assay, etc., if maximum volume is not exceeded.

Please note that tubes and media may be substituted based on availability with the permission of the PI or laboratory investigator.

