## 10 STATISTICAL CONSIDERATIONS

### 10.1 OBJECTIVES AND ENDPOINTS

OBJECTIVES	ENDPOINTS	JUSTIFICATION FOR ENDPOINTS
Primary		
To determine the single agent antitumor activity (disease control rate) of the anti-superenhancer agent Minnelide in participants with advanced, previously treated ASCP	Assess disease control rate in the study population, where disease control = best response of CR, PR or at least 16 weeks of stable disease	Establishing disease control in 8 or more of 25 participants with advanced previously treated ASCP would be considered clinically significant.
Secondary		
Determine Minnelide safety in participants with advanced, previously treated ASCP	Identify Adverse Events of grade 2 and above (per CTCAE criteria, version 5.0) related to Minnelide that occur from start of treatment to 30 days after last treatment.	Descriptive endpoint to assess toxicity profile of the study drug in this population.
	Assess rate of Serious Adverse Events related to Minnelide that occur from start of treatment to 30 days after last treatment.	
Assess alternative measures of anti- tumor activity	Determine median time until disease progression, switch to a new systemic treatment or death in the treated population. Data cut-off will occur 1 year after last Minnelide treatment.	Descriptive endpoints that may help to determine sample size needed for future Phase 3 study
	Determine median time until death in the treated population. Data cut-off will occur 1 year after last Minnelide treatment.	
	Determine objective response rate of Minnelide.	

OBJECTIVES	ENDPOINTS	JUSTIFICATION FOR ENDPOINTS
Exploratory		
Identify factors that influence participant response to treatment through detailed molecular analysis of participant tumor, serum and blood cell samples acquired at baseline, on-treatment and at time of progression	For each patient with available samples, we will describe the following properties and consider associations with patient response to therapy:	These endpoints have been selected to help understand why the drug may or may not work, to allow better design of future studies in this patient population.
	Tumor genetic mutations at baseline and at time of progression	Do specific genetic profiles give a patient higher or lower likelihood or response? Does treatment change mutational profile?
	Treatment-related change (between pre-treatment baseline and ~C1D15) in:	

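### The two rules for sharing out a scarce progression biopsy conflict: Section 5.2 ranks PDX/organoid models first, Section 5.1.3.6 last, and the exploratory tumor-mutation endpoint can lose data

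*Combined protocol and SAP*

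**What the plan says.** Three places in the protocol govern how the progression biopsy is divided.

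- **Section 5.1.3** sets the general rule for a biopsy too small for all assays: "priority will be given to completing the analyses listed first in the" Specimen Collection Table.
- **Section 5.2** is that table. Its assay column is headed "Test/assay (listed in order of precedence)", and the row for optional fresh tissue at progression reads "PDX/ organoid model generation Tumor mutational analysis WES or WGS on selected" (samples). The amount for the row is two 18-gauge cores.
- **Section 5.1.3.6** says that PDX/organoid models will be made "if residual tissue remains after other analyses are completed".

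Section 10.1 states what the tissue is for. One exploratory endpoint is "Tumor genetic mutations at baseline and at time of progression", and one of the questions beside it is "Does treatment change mutational profile"? The remaining tissue endpoints come under the heading "Treatment-related change (between pre-treatment baseline and ~C1D15) in".

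**The concern.** For a progression biopsy too small for everything, staff who follow the table spend tissue on PDX/organoid models before mutational analysis. Staff who follow Section 5.1.3.6 do the reverse. Both cannot be obeyed, and consumed tissue cannot be recovered.

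At stake is the second half of a paired comparison. The question of whether treatment alters the mutational profile needs a tumor result at baseline and another at progression. If the progression cores go to model generation and nothing is left, that participant contributes no tumor pair. The trial aims for up to 25 evaluable participants (Section 3.1) and the biopsy is optional, so few pairs can be expected in any case.

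**Working it through.** No error rate or sample size is involved. The check sets the passages side by side and counts entries.

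**1. Position of each assay under the two rules (progression sample)**

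| Assay | Order in Section 5.2 | Order under Section 5.1.3.6 |
|---|---|---|
| PDX/organoid generation | 1st of 3 | last |
| Tumor mutational analysis | 2nd of 3 | before PDX/organoid |
| WES/WGS on selected samples | 3rd of 3 | before PDX/organoid |

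**2. Do both rules reach the same sample?** Section 5.2 has three tumor-tissue rows: archival or fresh tissue at baseline, fresh tissue at baseline and Cycle 1 Day 15, and fresh tissue at progression. PDX/organoid work appears in 1 of the 3, the progression row. The only other analyses in that row are mutational analysis and WES/WGS, so these are what a residual-tissue condition would have to protect there.

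**3. Is the row order an artifact of the broken table?** Probably not. The location column of the same row runs TGen, NCI LP, BPC (to be decided). PDX/organoid models are made at TGen (Section 5.1.3.6) and mutational analysis is done at NCI LP (Section 5.1.2), so the locations follow the same order as the assays.

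**4. Comparison with the baseline row.** There, mutational analysis is 1st of 2, and residual-only use is marked explicitly with "If sufficient tissue available after other analyses below". The table therefore has a way of showing that an assay waits for leftover tissue. The progression row, as extracted, shows no such mark for PDX/organoid work.

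**5. Which endpoints depend on the progression biopsy?** Tissue endpoints in Section 10.1:

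| Tissue endpoint | Uses progression biopsy? |
|---|---|
| Tumor mutations | yes |
| Myc protein | no (baseline to about C1D15) |
| HSP70 protein | no (same) |
| Chromatin accessibility | no (same) |
| Tumor-infiltrating immune cells | no (same) |
| Tumor-associated cell milieu | no (same) |

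The total is 1 + 5 = 6, of which 1 uses the progression biopsy. Two numbered items in that list, circulating cytokines and circulating immune cell subsets, add a progression time point, but both are blood measures. None of the six endpoints is measured on PDX or organoid models.

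**6. Result.** The table ranks an assay that serves no Section 10.1 endpoint above the assay that supplies the one tissue endpoint needing this biopsy. Section 5.1.3.6 ranks them the other way.

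**The case against.** The strongest reply is that the two rules may govern different tissue. Section 5.1.3.6 names no time point and follows five assay descriptions (5.1.3.1 to 5.1.3.5) that Section 5.2 assigns to the baseline and Cycle 1 Day 15 cores. Its residual tissue could be what remains of those, with the progression row setting its own order. The weakness is that Section 5.2 plans no PDX/organoid work at baseline or Cycle 1 Day 15, so on this reading the condition governs nothing in the table.

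Further points:

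- **Scope of the Section 5.1.3 rule.** It speaks of assays described after it, and mutational analysis is described before it, in Section 5.1.2. That narrows the sentence, but the column heading in Section 5.2 sets precedence on its own, so the conflict stays.
- **Lost table text.** The row is cut off in extraction, and a condition on PDX/organoid work could have been lost. This weakens the comparison with the baseline row. It does not affect the assay order.
- **The lab manual.** Sections 5.1 and 5.1.3 send handling details to a Trial Lab Manual that is not available here and may settle the order. It would not correct the protocol text.
- **Shortage is hypothetical.** Section 5.1.3 plans about 5 passes per biopsy against 2 cores in the row, so there may be tissue to spare. This stands: how often tissue runs short is unknown.
- **PDX first may be intended.** Section 5.1.3.6 says the models may help explain resistance, and Section 1.1.3 includes tissue at progression among its exploratory aims. The protocol does not state which order was meant. If PDX first is deliberate, Section 5.1.3.6 is the text that needs changing.
- **Backup data.** ctDNA and circulating tumor cells are drawn at progression, and both can give mutation data (the cells only if sufficient; Section 5.1.1.2). Neither supplies the tumor result.

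**Conclusion.** The concern holds, as a minor point for the sponsor to consider. The protocol gives opposite orders for the same specimen, and the alternative readings do not remove the conflict.

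The consequence is small. It needs a participant who accepts the optional biopsy and a sample too small for all three assays. The endpoint is exploratory, is limited to patients with available samples, and is to be analyzed first by descriptive methods (Section 10.5.9). The number of results lost cannot be estimated from the protocol. The primary endpoint, the two-stage design and the secondary endpoints are unaffected.

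The conclusion rests on two assumptions: that the assay order in the extracted row is the true order, which the location column supports, and that Section 5.1.3.6 applies to the progression sample, the only one for which Section 5.2 plans PDX/organoid work.

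**What to change.** In the progression row of Section 5.2, list tumor mutational analysis first, WES/WGS on selected samples second and PDX/organoid generation last. Beside PDX/organoid generation, add the baseline row's residual-tissue condition, without its final word because nothing would stand below it. This brings the table into line with Section 5.1.3.6 and protects the one Section 10.1 tissue endpoint that uses the biopsy. If the sponsor does want PDX/organoid models first, Section 5.1.3.6 should be amended instead and the possible loss for the mutation endpoint accepted openly.

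The cost is one reordered row and one short phrase. The core amount, the number of passes and the study calendar stay as they are. The downside is possibly fewer PDX/organoid models when tissue is short, and so less material for studying resistance. The change should be made before further progression biopsies are divided.

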#### 5.1.3.1 IHC Studies

IHC analysis will be performed by collaborators at TGen to determine the expression of MYC and other super-enhancer regulated genes such as HSP70 and COL1A2 in samples from Minnelide treated participants.

## 5.1.3.2 Assay for Transposase Accessible Chromatin using sequencing (ATAC-seq)

ATAC-seq analysis will be performed by collaborators at TGen in samples from Minnelide treated participants to determine effects of Minnelide treatment on chromatin accessibility.

## 5.1.3.3 Multiplex IHC for immune cells

Changes in the profile of immune cells infiltrating the tumor following Minnelide treatment will be assessed by the [name]/ [name] lab(s). Tumor biopsies will also be analyzed by multiplexed, multispectral IHC and assessed for immune subsets, include including MDSCs, Tregs, CD4+ or CD8+ T cells, and M1/M2 tumor-associated macrophages (TAMs). If there are sufficient samples, functional markers such as PD1, PDL1, Tim3, CTLA4 and CD40 may also be included.

## 5.1.3.4 Digital Spatial Genomics

Digital spatial genomics will be performed at TGen on selected samples to determine the effects of Minnelide treatment on the localization of different cell populations within the tumor microenvironment.

#### 5.1.3.5 Single cell RNA-seq

Single cell RNA-seq will be performed by collaborators at TGen on selected samples to determine changes in cell population composition and cell state within the ASCP tumor microenvironment upon Minnelide treatment.

## 5.1.3.6 Establishment of participant-derived xenograft (PDX) and organoid models

PDX/Organoid models will be established by collaborators at TGen if residual tissue remains after other analyses are completed. Those models will be used to study the biology of ASCP and test new therapeutic regimens for ASCP and may also be used to help understand mechanisms of resistance to Minnelide.

# 5.2 SPECIMEN COLLECTION TABLE

Specimen Type	Test/assay (listed in order of precedence)	Specimen Type (Amount)	Collection (timepoints)	Location of specimen analysis^ (CCR lab database, if applicable)	
Archival or fresh tumor tissue obtained at any time prior to start of study. FFPE acceptable. If multiple acceptable specimens are available, analysis should be completed with the most recent.  (Optional)	Tumor mutational analysis WES or WGS on selected	10-unstained slides If sufficient tissue available after other analyses below	Baseline	NCI LP BPC (TBD*) (Labmatrix)	
Fresh tumor tissue (Optional)	IHC for PD biomarkers ATAC-seq Multiplex IHC for immune cell changes Digital spatial genomics and/ or single cell RNA-seq	Unstained slides; or, 5-18 gauge cores at each timepoint	Baseline Cycle 1 Day 15 (±7 days)	TGen [name]/ [name] (Labmatrix)	
Fresh tumor tissue (Optional)	PDX/ organoid model generation Tumor mutational analysis WES or WGS on selected	2-18g cores	At the time of disease progression	TGen NCI LP BPC (TBD*) (Labmatrix)	

Version Date: 7/10/2025

Specimen Type	Test/assay (listed in order of precedence)	Specimen Type (Amount)	Collection (timepoints)	Location of specimen analysis^ (CCR lab database, if applicable)
Serum	Cytokine markers	1- 4 mL red SST tubes at each timepoint	Baseline Cycle 1 Day 15 (±7 days) At the time of disease progression	BPC ([name]) (Labmatrix)
Blood	ctDNA	1- Streck 10-cc Cell- Free DNA BCT tube for each timepoint	Baseline Cycle 1 Day 15 (±7 days) Cycle 2 Day 1 (±3 days) At the time of disease progression	Developmental Therapeutics Branch Clinical Translation Unit (DTBCTU) (Labmatrix)
Blood	CTCs	2- Streck 10-cc Cell- Free DNA BCT tubes at each timepoint	Baseline Cycle 1 Day 15 (±7 days) Cycle 2 Day 1 (±3 days) At the time of disease progression	DTBCTU (Labmatrix)
PBMC	Immune cell subset profiling by flow cytometry	2 - 10 cc sodium heparin (green top) at each timepoint	Baseline Cycle 1 Day 15 (±7 days)	[name] (Labmatrix)

\*Laboratory for planned analyses has not been finalized. Samples to be retained by the Biospecimen Processing Core (BPC) until distribution. Tube size for bloods may be adjusted based on supply available or change in assay, etc., if maximum volume is not exceeded.

Please note that tubes and media may be substituted based on availability with the permission of the PI or laboratory investigator.

^ The location of specimen processing or analysis may be adjusted with the permission of the PI or laboratory investigator

Version Date: 7/10/2025

#### 5.3 SAMPLE STORAGE, TRACKING AND DISPOSITION

Samples will be ordered in CRIS and tracked through a Clinical Trial Data Management system. Should a CRIS screen not be available, the CRIS downtime procedures will be followed. Samples will not be sent outside NIH without appropriate approvals and/or agreements, if required.

## 5.3.1 Biospecimen Processing Core (BPC)

## 5.3.1.1 Handling and Processing of Specimens

The samples will be placed immediately on wet ice and refrigerated. The date and exact time of each blood draw should be recorded on the sample tube.

For sample pickup, page .

For immediate help, call (main BPC number) or, if no answer, (main clinical pharmacology lab number).

For questions regarding sample processing, contact [contact].

## 5.3.1.2 Biospecimen Processing Core

All samples sent to the BPC will be barcoded, with data entered and stored in the Labmatrix utilized by the BPC. This is a secure program, with access to Labmatrix limited to defined BPC personnel, who are issued individual user accounts. Installation of Labmatrix is limited to computers specified by BPC. These computers all have a password restricted login screen. All BPC personnel with access to participant information complete the NIH online Protection of Human Subjects course.

Labmatrix creates a unique barcode ID for every sample and sample box, which cannot be traced back to participants without Labmatrix access. The data recorded for each sample includes the participant ID, name, trial name/protocol number, time drawn, cycle time point, dose, material type, as well as box and freezer location. Participant demographics associated with the clinical center participant number are provided in the system. For each sample, there are notes associated with the processing method (delay in sample processing, storage conditions on the ward, etc.).

Barcoded samples are stored in barcoded boxes in a locked freezer at either -20 or -80°C according to stability requirements. These freezers are located onsite in the BPC and offsite at NCI Frederick Central Repository Services in Frederick, MD. Visitors to the laboratory are required to be accompanied by laboratory staff at all times.

Access to stored clinical samples is restricted. Samples will be stored until requested by a researcher named on the protocol. All requests are monitored and tracked in Labmatrix. All researchers are required to sign a form stating that the samples are only to be used for research purposes associated with this trial (as per the IRB approved protocol) and that any unused samples must be returned to the BPC. It is the responsibility of the NCI Principal Investigator to ensure that the samples requested are being used in a manner consistent with IRB approval.

Following completion of this study, samples will remain in storage as detailed above. Access to these samples will only be granted following IRB approval of an additional protocol, granting the rights to use the material.

All specimens obtained in the protocol are used as defined in the protocol. Any specimens that are remaining at the completion of the protocol will be stored in the conditions described below. The

Version Date: 7/10/2025

study will remain open so long as sample or data analysis continues. Samples from consenting participants will be stored until they are no longer of scientific value or if a participant withdraws consent for their continued use, at which time they will be destroyed. If, at any time, a participant withdraws consent, the participants data will be excluded from future distributions, but data that have already been distributed for approved research use will not be able to be retrieved. The PI will record any loss or unanticipated destruction of samples as a deviation. Reporting will be per the requirements of Section 7.2.

Sample barcodes are linked to participant demographics and limited clinical information. This information will only be provided to investigators listed on this protocol, via registered use of the Labmatrix. It is critical that the sample remains linked to participant information such as race, age, dates of diagnosis and death, and histological information about the tumor, in order to correlate genotype with these variables.

Note: All other CCR lab systems/databases at which samples will be stored/analyzed are as noted in the Specimen Collection Table (e.g., Labmatrix; Section 5.2).

